Phase I Dose Escalation Trial of Hypofractionated Radiosurgery for Large Brain Metastases

Principal Investigator

[name]

Co-investigators

[name]

[name]

[name], PhD

[name]

[name]

[name]

[name]

[name]

[name], MS

Department of Radiation Oncology
Winship Cancer Institute of Emory University

Precis

Hypofractionated Radiosurgery (HR) is a treatment option for delivering focal brain radiation therapy to patients with brain metastases, who would otherwise not be candidates for single fraction stereotactic radiosurgery (SRS) based on size criteria. The optimal dose and fractionation schedule for HR is undefined. We propose a phase I dose escalation trial of HR delivered in 5 fractions, with a minimum of 2 and a maximum of 3 fractions being delivered per week, to patients with brain metastases or resection cavity greater than 3cm and less than 6cm. Dose escalation will proceed according to the Escalation with Overdose Control (EWOC) method with a planned total enrollment of 24 patients, in 8 patient cohorts with 3 patients per cohort. A 4 month observation period will occur for each completed cohort prior to dose escalation, with a goal timeline for trial completion of 4 years from first patient enrollment

1.0 INTRODUCTION/BACKGROUND

Brain metastases are the most common adult intracranial tumor, occurring in up to 40% of adult cancer patients, and represent an important cause of morbidity and mortality in this population¹. The treatment of brain metastases may involve surgery followed by radiotherapy or radiotherapy alone²⁻³. There are multiple options for radiotherapy; including whole brain radiation (WBRT), whole brain radiation combined with stereotactic radiosurgery (SRS), or focal brain radiation with SRS alone. Level I and level II evidence, supports the use of SRS in multiple settings. Randomized controlled trials have shown the addition of SRS to WBRT leads to a significant increase in median survival and time to recurrence compared with WBRT alone for patients with solid single brain metastasis and a KPS >70³⁻⁵. Stereotactic radiosurgery combined with WBRT is also supported as an alternative to resection plus WBRT for metastatic lesions < 3cm, as multiple retrospective cohort studies have shown relatively equivalent survival rates⁶⁻⁸. Focal brain radiation by SRS alone is commonly used as salvage therapy for patients who recur with brain metastasis after WBRT, and is also increasingly used as a primary treatment modality in attempts to prevent or delay the known neurocognitive toxicities of WBRT⁹. One randomized controlled trial and multiple retrospective cohorts report equivalent survival results with SRS alone when compared to SRS plus WBRT or WBRT alone^{2, 10-12}. The data supporting SRS for intact brain metastasis is commonly extrapolated to support the use of SRS to resection cavities for improved local control following surgical resection of intracranial metastasis. Multiple published series have reported on the use of SRS in this setting and have demonstrates local control rates of 70 - 94% with additional benefits over WBRT including short treatment course and improved patient compliance¹³. Clearly, SRS is an effective and important tool for the treatment of brain metastasis in multiple clinical settings.

Stereotactic Radiosurgery, as defined by the American Society for Therapeutic Radiology and Oncology (ASTRO), the American Association of Neurological Surgeons (AANS), and the Congress of Neurological Surgeons (CNS), includes single dose SRS and well as HR delivered in 2-5 fractions over multiple days¹⁴⁻¹⁵. The majority of data supporting the use of SRS for the treatment of brain metastases has evaluated only single dose SRS and it is unclear whether the same results can be attributed to HR in 2-5 fractions. Brain metastasis amenable to single fraction SRS are typically defined as those measuring less than 3cm and producing less than 1cm of midline shift³. For brain metastasis not amenable to SRS, but for which focal brain radiation is indicated for boost or as salvage after WBRT or for avoidance of neurocognitive decline, HR provides an alternative treatment option. Current data describing the use and results of HR for the treatment of brain metastasis is limited to few retrospective series. Pater and colleagues from University of Cincinnati have demonstrated HR delivered to a dose of 30 Gy in 5 fractions to be effective and tolerable in a series of 34 patients, with a 6% (n=2) incidence of asymptomatic radiation necrosis and a 6 month actuarial local control rate of 68%¹⁶. A second series of 43 patients with metastatic breast cancer treated at Staten Island University Hospital utilized HR to a dose of 24 Gy delivered in 4 fractions, with a median survival from treatment of 7.5 months¹⁷. Recently, Wang et al. have reported on the use of HR in the setting of resected brain metastasis with resection cavities > 3cm and have demonstrated a local control rate of 80% at 6 months with the use of 24 Gy in 3 daily fraction¹⁸. With only a few series reported, the optimal dose and fractionation schedule is unknown.

In our own experience at Emory¹⁹ with 47 patients receiving HR for both solid intact metastasis (22) and resection cavities (25), we have demonstrated 6 month and 1 year LC rates of 69% (CI 0.62-0.77) and 59% (CI 0.67 – 0.50), with 3 (6.4%) patients experiencing symptomatic radiation necrosis. On multivariate Cox-regression analysis, improved local control was associated with smaller planned target volume (PTV) volume (SS, $p=0.02$) and higher dose per fraction (NS, $p=0.06$). No significant association was found between LC and previous RT received, resection cavity vs. solid tumor, total dose, biological equivalent dose (BED) or single fraction equivalent dose (SFED). These results show HR is well tolerated in both new and recurrent, previously irradiated large intact or resected brain metastases. Significantly higher rates of local failure are observed with larger PTV volumes suggesting a need for dose escalation when using HR for large intracranial lesions.

We propose a prospective phase I trial for patients with solid brain metastasis greater than 3cm and less than 6 cm, who have either had no treatment or who are status post surgical resection. The purpose of this trial will be to determine the maximum tolerated dose for fractionated radiosurgery delivered in 5 fractions with a minimum of 2 and a maximum of 3 fractions being delivered per week. Results from this trial may form the basis of future trials evaluating the efficacy of fractionated radiosurgery regimens for local and distant control of brain metastasis and for directly comparing WBRT with FRS, for patients not amenable to single fraction SRS. Such a phase III study would answer the question about as to whether local irradiation is adequate treatment for patients with large brain metastasis.

2.0 OBJECTIVES

To demonstrate the safety and feasibility of treating brain metastases or resection cavities greater than 3cm with hypofractionated radiosurgery and to determine the maximum-tolerated radiation dose for HR delivered in 5 fractions, 2-3 fractions per week.

2.1 Primary Endpoints:

2.1.1 Maximum tolerated dose (MTD)

2.1.2 Dose limiting toxicity (DLT): any acute or late CNS toxicity with grade greater than or equal to 3 with attribution score greater than or equal to 3.

2.2 Secondary Endpoints:

2.2.1 Local control: lack of progression of disease in resection cavity

2.2.2 Distant control: lack of progression of disease in surrounding brain

2.2.3 Overall survival: death from any cause

2.2.4 Long-term neurocognitive outcomes: using the Hopkins Verbal Learning Test–Revised (HVLT-R), Mini Mental Status Exam (MMSE) and Cognitive Functioning Subscale of the Medical Outcomes Scale (MOS).

2.2.5 Quality of life (QOL) outcomes: using the quality of life questionnaire for the Functional Assessment of Cancer Therapy-Brain (FACT-Br).

3.0 STUDY DESIGN AND METHODS

3.1 Registration

Patients with a metastatic brain tumor or resection cavity greater than 3cm and less than 6cm who are referred for radiation therapy to the brain, who meet the inclusion criteria listed below, and who have signed formal consent for participation in this clinical trial

will be enrolled into the radiation therapy dose group according to the escalation with overdose control design described below.

3.2 Enrollment/Randomization

This study will include 8 patient cohorts with 3 patients per cohort. The patients will be enrolled and treated following a Bayesian method permitting precise determination of the therapeutic working-dose while directly controlling the likelihood of an overdose. The method, known as Escalation with Overdose Control (EWOC), has been used to design phase I clinical trials at several cancer centers including the Fox Chase Cancer Center (PA), the Sylvester Comprehensive Cancer Center (FL), and the Winship Cancer Institute (GA) and pharmaceutical companies. EWOC was the first dose-finding procedure to directly incorporate the ethical constraint of minimizing the chance of treating patients at unacceptably high doses. Its defining property is that the expected proportion of patients treated at doses above the MTD is equal to a specified value α , the feasibility bound. This value is selected by the clinician and reflects his/her level of concern about overdosing.

The dose levels for the trial are summarized in Table 1. The dose for the first cohort of 3 patients in the trial will be the dose level 0, previous results indicating this to be a safe dose. The patient accrual will be suspended until the 4 month toxicity evaluation is completed for all previously enrolled patients. The dose for each subsequent cohort of 3 patients will be determined so that, on the basis of all available data and the target highest acceptable toxicity level of 25% DLT, the probability that it exceeds the MTD is equal to a pre-specified value α . In this trial, we set $\alpha = 0.25$ and increase α in small increments until $\alpha = 0.5$, this value being a compromise between the therapeutic aspect of the agent and its toxic side effects. The dose selected for every patient in the trial will be between the minimum dose of 27.5 Gy and the maximum allowable dose of 40 Gy. The trial will be terminated if 3 DLTs are observed in any cohort of 3 patients treated with the lowest dose level. The trial will stop after 24 patients have been enrolled and MTD will be estimated from one of the 6 specified dose levels listed in the Table 1. If no MTD is found because even the highest dose level is still considered under toxic, then the highest dose group will be considered the MTD and expanded to 12 patients.

The enrollment will be done sequentially. If a grade 5 toxicity develops in the initial evaluation period (4 months), then the study will be halted and all patient data will be reviewed by the data safety monitoring committee to determine the likelihood that the treatment given was responsible and whether the study can resume. If a patient is not able to complete follow up to the toxicity assessment point of 4 months due to a toxicity judged not to be at least possibly related to therapy, then that patient will be replaced at the same dose level by the next patient enrolled into that cohort. After all patients in a designated dose group have completed the 4 month toxicity assessment, the documented DLTs, having previously been reviewed by the PI, co-investigators and data safety monitoring committee, will be again reviewed by the PI and co-investigators at the time the decision is made to escalate or de-escalate to the next dose level accordingly.

Example of sequential enrollment

Patients identified meeting eligibility criteria will be offered enrollment in this study. As with any other protocol, the risks, benefits, and alternatives of protocol enrollment will be

thoroughly discussed and patient consent form will be provided for further information. Once the patient agrees to be enrolled, they will be allocated to a specific dose level based on sequential enrollment. The first three patients assigned will be enrolled into dose level 1. Once this group has reached the accrual goal of three patients, then that cohort will be closed until the 4 month toxicity evaluation is completed for all 3 patients. The next three consecutive patients within that cohort will be enrolled to dose level 2 unless a grade 3 or 4 toxicity was documented (as detailed above). If there was such a toxicity, then the three next patients will be enrolled into the same dose level as an expansion.

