3.8.1 Neurologic Toxicity Assessment

1. Neurologic/CNS Toxicity will be graded according to the Common Toxicity Criteria for Adverse Events (CTCAE) version 4.03 (**Appendix B**).
2. Toxicity assessment will be made during treatment at weekly MD visits and at each follow up (1 month and 4 months after completion of radiation therapy, and every 3 months thereafter). A plus or minus 3 week window will be allowed for follow-up assessments.
3. Toxicity will be classified as immediate (within 24 hours of treatment), acute (within 4 months), or chronic (more than 4 months) based on timing after SRS.
4. Toxicities of any grade should be recorded by the radiation oncology staff on the study specific case report form at the prespecified assessment time points. All \geq grade 3 nervous system toxicity will be reported to the study principle investigator (PI).
5. Toxicities attributed to chemotherapy recorded by medical oncology staff will not be captured as study related AEs.
6. Attribution will initially be scored by the study investigators on the case report form and/or the physician seeing the patient in follow-up visit on a five point scale: 5=definitely caused by radiation treatment, 4= probably caused by radiation treatment, 3=possibly caused by radiation treatment, 2= probably not caused by radiation treatment, 1= not due to radiation treatment. Attribution will be reviewed by the PI and co-investigators. Any \geq grade 3 CNS toxicity with attribution ≥ 3 will be considered at DLT and will be reported to the DSMC. If a grade 3 CNS toxicity occurs after the patients is considered off study this will not be considered a DLT.
7. Any grade 5 toxicity will halt the study for review by the DSMC and IRB.
8. Maximal Tolerated Dose (MTD)
The MTD will be defined as the highest dose level where a grade 3 or greater with an attribution score of ≥ 3 develops in ≤ 2 of 6 patients in a dose group within 4 months of the treatment.
9. Laboratory values are not required for this protocol and will not be collected.

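### The only DLT-count termination rule looks at one cohort of three at a time, so pooled DLTs at the lowest dose level can never stop the trial

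*Combined protocol and SAP*

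**What the plan says.** Section 3.2 contains the rule: "The trial will be terminated if 3 DLTs are observed in any cohort of 3 patients treated with the lowest dose level". The same section chooses each later dose "on the basis of all available data and the target highest acceptable toxicity level of 25% DLT", and confines every dose to the range "between the minimum dose of 27.5 Gy and the maximum allowable dose of 40 Gy". Table 1 shows 27.5 Gy as level -1, and "The dose for the first cohort of 3 patients in the trial will be the dose level 0". The size is fixed: "This study will include 8 patient cohorts with 3 patients per cohort" and "The trial will stop after 24 patients have been enrolled". Section 3.2 then has the MTD estimated as one of the six tabulated levels. It says what to do if even the top level is not toxic enough, but not what to do if even the bottom level is too toxic.

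Other controls exist. Accrual pauses for the 4-month evaluation of all earlier patients. Section 3.2 has DLTs reviewed by the investigators and the DSMC, and by the investigators again before each dose decision. Section 3.8.1 sends each DLT to the DSMC and adds "Any grade 5 toxicity will halt the study for review by the DSMC and IRB". Section 6 halts the study for a death at least possibly related to treatment and lets the investigator halt it at discretion. Section 7.2.4 gives the DSMC periodic summaries. None of these sets a limit on the number of DLTs.

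**The concern.** The plan pools all data to choose a dose but not to decide whether any dose is acceptable. If the lowest level is itself too toxic, the evidence will usually be spread over several cohorts, and the rule cannot see it. After 4 DLTs in 6 patients, split two and two, the evidence against a 25% rate is already strong and nothing is triggered.

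The dosing model does not clearly fill the gap. The dose cannot go below 27.5 Gy, and the text gives no instruction for a model that places the MTD below that floor. At stake is how many patients are treated at a level well above the stated acceptable rate before a pre-specified rule ends the trial, and what is then reported as the MTD.

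**Working it through.** **Inputs (section 3.2).** Cohort size 3; eight cohorts; 8 × 3 = 24, which reproduces the fixed sample size. The first cohort is at level 0, so at most 8 − 1 = 7 cohorts can be at level -1. The highest acceptable DLT rate is 25%. The documents give no stopping probability for the rule, so there is no planned figure to reproduce for it.

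**Present rule.** With true DLT rate p at the lowest level, one cohort triggers with probability p³. Over k such cohorts, P(stop) = 1 − (1 − p³)^k. Expected patients at that level over at most seven cohorts are 3 × [1 − (1 − p³)^7] / p³.

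| p | p³ | k = 3 | k = 7 | Expected patients, of 21 |
|---|---|---|---|---|
| 25% | 1.6% | 5% | 10% | 20.0 |
| 40% | 6.4% | 18% | 37% | 17.4 |
| 50% | 12.5% | 33% | 61% | 14.6 |
| 60% | 21.6% | 52% | 82% | 11.4 |

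For example, at 50% with k = 3: 1 − 0.875³ = 33%. Over seven cohorts, stopping is more likely than not only once p exceeds about 45.5%; over three cohorts, about 59%.

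**What the rule cannot see.** Two DLTs in each of seven cohorts is 14/21 with no trigger. Under a Beta(1,1) prior the posterior is Beta(1 + x, 1 + n − x). P(rate > 25%) is then 0.987 at 4/6 and above 0.9999 at 14/21.

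**Fewer cohorts at the floor.** Seven is the maximum exposure. A two-parameter logistic EWOC was simulated with 20,000 trials per setting. Its assumptions, which the documents do not supply, were:
- uniform priors (DLT probability at 27.5 Gy on 0–0.25; MTD on 27.5–40 Gy);
- no level skipped;
- α either fixed at 0.25 or raised by 0.05 per cohort to 0.5 (the plan says only "in small increments until");
- a DLT rate rising 0, 5 or 10 points per level.

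The present rule then stopped 14–31% of trials at 40%, 36–57% at 50% and 64–80% at 60%. At 50% about 18.5–20 patients were treated in total, with about 10 DLTs; at 60%, about 15–17 patients.

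**A cumulative boundary.** Stop when P(rate > 25% | all patients at the lowest level) > 0.95, checked after each cohort there. Beta(1,1), Beta(0.5,1.5) and Beta(0.25,0.75) priors all give 3/3, 4/6, 5/9, 6/12, 7/15, 8/18, 9/21. Stopping probabilities come from an exact recursion: carry forward the probability of each DLT total not yet stopped, convolve with Binomial(3, p), and remove totals at or above the boundary. For both rules together, also remove any cohort with 3/3.

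| p | Present rule | Cumulative only | Both rules |
|---|---|---|---|
| 15% | 2% | 2% | 3% |
| 25% | 10% | 13% | 17% |
| 40% | 37% | 58% | 63% |
| 50% | 61% | 86% | 88% |
| 60% | 82% | 98% | 98% |

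These are for seven lowest-level cohorts. With the cumulative rule alone, expected patients at that level are 19.7, 15.1, 11.3 and 8.2 at 25%, 40%, 50% and 60%.

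**The case against.** A reader might infer that the rule usually fails whenever the lowest dose is far too toxic. The figures do not support that. At 50% the outcome is near even and depends on how many cohorts reach the floor; at 60% or more the rule usually stops the trial, though late.

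A reader might also infer that accumulated toxicity goes unexamined. It does not: dosing uses all the data, accrual pauses between cohorts, and the DSMC and investigators review DLTs. A count of 4/6 would be seen. What stands is that nobody is told in advance what count ends the trial.

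It is also tempting to say that the plan orders continued enrolment at the floor and will still declare an MTD there. Neither is stated. The case where no permitted dose satisfies the overdose constraint is simply not addressed. Section 3.8.1 defines the MTD as the highest level with DLTs in at most 2 of 6 patients, which 4/6 fails, whereas section 3.2 requires an estimate from the six tabulated levels. The two conflict.

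Finally, the scenario may be unlikely. The background section reports asymptomatic necrosis in 6% of 34 patients at 30 Gy in five fractions, and symptomatic necrosis in 3 of 47 in the institution's own series. These are not the DLT endpoint and do not exclude higher rates, but they make 40–50% at a lower dose look remote. That lowers the urgency, but a safety rule exists for the unlikely case. A cumulative rule is not powerful early either: with three cohorts at 40% it stops about 30% of trials, against 18% now.

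**Conclusion.** The point holds as a gap in pre-specified safety stopping. The only DLT-count rule does not pool cohorts and is weak at moderate excess toxicity: 37% stopping at a 40% rate and 61% at 50% under maximum exposure, 18% and 33% over three cohorts. There is no rule for an MTD below 27.5 Gy, and the two MTD statements disagree in that case.

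The stopping figures for the present rule need only independent patients with a common DLT rate at the lowest level. The simulated ranges rest on assumed priors, increments and slopes. The lowest level is read as level -1. If it meant the lowest level actually opened, eight cohorts could count and stopping would be 41% at 40% and 66% at 50%, which leaves the conclusion unchanged. The change is worth making; the existing reviews mean that it does not describe an unmonitored trial.

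**What to change.** Add to section 3.2 a cumulative boundary on all patients treated at the lowest level, checked at each existing 4-month cohort review: terminate when the posterior probability that the DLT rate exceeds 25% is above 0.95, that is at 3/3, 4/6, 5/9, 6/12, 7/15, 8/18 or 9/21. State that no MTD is declared if it is met, and reconcile section 3.2 with the MTD definition in section 3.8.1 accordingly. State also what follows if the model places the MTD below the floor.

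The choice between adding and replacing should be explicit:
- **Replacing the 3-of-3 rule** raises false stopping at exactly 25% over seven cohorts from 10% to 13%. It also gives up a present safeguard: 0/3 followed by 3/3 is 3/6, below the 4/6 boundary, and would no longer stop the trial.
- **Adding it alongside** keeps that safeguard. False stopping becomes 17% at 25% and 3% at 15%.

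The 0.95 threshold is a choice. With a Beta(1,1) prior, 0.90 would raise stopping under the cumulative rule alone to 80% at 40%, but false stopping at 25% to 35%. The boundary uses lowest-level patients only; DLTs at higher levels still enter through the dosing model. The cost is a sentence or two of text, with no added visits and no added delay, because accrual already pauses for each review.

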5.2 Sample size

Dose escalation on this study will be using EWOC design. There will be 3 patients per dose escalation and enrollment will be done sequentially. A **fixed sample size of 24 will be used.**

If a patient is not able to complete follow up to the toxicity assessment point of 4 months due to a toxicity judged not to be at least possibly related to therapy, then that patient will be replaced at the same dose level by the next patient enrolled into that cohort.

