5.3 Statistical Analysis

5.3.1 Primary Analysis: The rate of toxicities at 4 months will be calculated with 95% confidence interval (CI).

5.3.2 Secondary Analysis:

5.3.2.1 The median time to local/distant brain progression will be calculated by Kaplan-Meier method with 95% CI. For a given time point, say 4 month, the rate of local/distant progression will be calculated with 95%CI.

5.3.2.2 The median of OS time with 95% CI will be calculated by Kaplan-Meier method.

5.3.2.3 Neurocognitive effect and QOL outcomes will be regressed over time using GEE model. The population change over time (slope) will be estimated with 95%CI.

5.3.3 Patient Stratification: All enrolled patients will proceed through dose escalation as a single cohort, however patients will be analyzed as separate strata, should enrollment allow it, based on the following criteria.

5.3.3.1 Intact brain metastasis versus resection cavity.

5.3.3.2 No previous cranial irradiation versus previous WBRT or other cranial irradiation.

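### If 40 Gy is still under-toxic, section 3.2 can take enrolment to 27, 30 or 33 against a fixed 24, and it names 40 Gy the MTD before the added patients are assessed

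*Combined protocol and SAP*

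**What the plan says.** The precis gives a "planned total enrollment of 24 patients, in 8 patient cohorts with 3 patients per cohort". Section 5.2 says a "fixed sample size of 24 will be used". Section 3.2 agrees at first: "The trial will stop after 24 patients have been enrolled and MTD will be estimated from one of the 6 specified dose levels" in Table 1. It then adds a branch. The condition for entering it is worded "If no MTD is found because even the highest dose level is still considered under toxic". The consequence, given in the second half of that sentence, is a label and an enlargement: "then the highest dose group will be considered the MTD and expanded to 12 patients". Neither 5.2 nor the precis mentions that branch, and no section gives a larger maximum.

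Two statements bear on what MTD means. Section 3.2 doses against "the target highest acceptable toxicity level of 25% DLT". Section 3.8.1, item 8, defines the MTD as the highest level at which at most 2 of 6 patients have a qualifying toxicity within 4 months. For the primary analysis, 5.3.1 says "The rate of toxicities at 4 months will be calculated with 95% confidence interval (CI"), without saying whether this is done by dose level.

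**The concern.** There are two linked problems on one branch of the design.

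The first is size. The branch sentence comes after the stop at 24 and can require more patients, while the sample-size section calls 24 fixed. Anyone approving or resourcing the study from 5.2 or the precis would not know that more patients might be treated at the highest dose.

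The second is the label. The branch opens by saying that no MTD was found and ends by naming one. Against a 25% target, a dose judged under-toxic is the highest dose tested, not an estimate of the 25% dose. On the wording, the label is attached when the expansion begins, and nothing says what follows if the added patients have DLTs. The MTD is a primary endpoint (2.1.1, 5.1.1), and section 1.0 expects later trials to build on the result.

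**Working it through.** **Inputs.** Cohorts and cohort size: 8 and 3 (precis, 3.2). Stated total: 24 (precis, 3.2, 5.2). Expansion size at level 4: 12 (3.2). Observation per cohort: 4 months (precis, 3.2). DLT target: 25% (3.2). Starting level: 0 in the main text of 3.2, 1 in its worked example.

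**The plan's own figure.** 8 × 3 = 24, so the stated total reproduces.

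**Total after expansion.** Let m be the number of cohorts treated at level 4 when 24 patients are enrolled. Level 4 then holds 3m patients, and

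total = 24 + max(0, 12 − 3m).

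| m | At level 4 | Added | Total |
|---|---|---|---|
| 4 or more | 12 or more | 0 | 24 |
| 3 | 9 | 3 | 27 |
| 2 | 6 | 6 | 30 |
| 1 | 3 | 9 | 33 |

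The largest excess is 9/24 = 37.5%. This counts patients already at level 4 towards the 12 and leaves out replacements. With m = 0 the formula gives 36, but a level nobody has received could hardly be judged under-toxic, so 33 is the upper end.

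**Which paths give which total.** Starting at level 0 and moving one level per cohort, cohorts 1–4 use levels 0–3 (12 patients) and cohorts 5–8 use level 4 (12 patients): exactly 24. One, two or three repeated cohorts below level 4 give 27, 30 or 33. Starting at level 1, one repeat still gives 24, and two, three or four repeats give 27, 30 or 33. Section 3.2 states no rule against skipping levels. The formula depends only on m.

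**Time.** Eight cohorts need 8 × 4 = 32 months of observation. Nine extra patients make it 9 × 4 = 36 months if enrolled as one group, or 11 × 4 = 44 if observed in threes. All are inside the 48-month goal, with accrual time not counted.

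**What 12 patients can show.** Exact (Clopper–Pearson) two-sided 95% intervals:

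- 0/12: 0 to 1 − 0.025^(1/12) = 26.5%
- 1/12: 0.2% to 38.5%
- 2/12: 2.1% to 48.4%

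None excludes 25%. The one-sided 95% limit for 0/12, 1 − 0.05^(1/12) = 22.1%, would, so the type of interval has to be named. The target rate itself corresponds to 3/12.

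**The two MTD rules compared.** 2/6 = 33.3%, which is above 25%. If the true DLT rate were 40% (an assumed value), the chance of at most 2 of 6 is 0.6^6 + 6(0.4)(0.6^5) + 15(0.4^2)(0.6^4) = 0.047 + 0.187 + 0.311 = 0.54. Meeting the 3.8.1 rule therefore does not show that the 25% dose was located.

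**Frequency.** This needs inputs that the plan does not give. As an illustration only, assume a logistic EWOC model with uniform priors, α rising by 0.05 per cohort, no skipping, and true DLT rates of 10–15% at level 4 (300 simulated trials per scenario). With the MTD prior reaching 45–50 Gy, level 4 held 3–9 patients in about 26–40% of trials and 12 in about 40–73%. With the prior capped at 40 Gy, level 4 was never opened. These shares are not restricted to trials that would trigger the branch. They show only how far the answer depends on unstated inputs.

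**The case against.** The strongest reply concerns the label. Section 3.8.1 holds the only sentence that formally defines the MTD, and an under-toxic level 4 would usually satisfy it. Doses are capped at 40 Gy and the MTD must be one of six listed levels, so within that set the highest acceptable dose is 40 Gy. On this view 3.2 states an open convention, with its condition in the same sentence. Much of this stands. A reader might infer that the plan would report a false result, and the documents do not support that. They contain two MTD concepts that disagree on this branch. What remains is that 3.2, judged by its own target, says none was found and still names one, with no provision for DLTs among the added patients.

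On size, the reply is that the expansion is disclosed in 3.2, that steady escalation from level 0 fits 24 exactly, and that 33 requires level 4 to open only at the eighth cohort. All true. A reader might infer that the trial will overrun, but the documents show only that it can. The expansion could also be read as lying inside the 24; no text says so, and the sentence follows the stop at 24. No breach of the 4-year goal is shown.

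A reader might also infer that the EWOC prior must extend above 40 Gy so that the model itself can declare the MTD out of range. That does not follow. The prior also drives dosing, so changing it could change escalation. Nor would it be a reliable safeguard: under an assumed logistic model with uniform priors, 0/3 at each of levels 0–3 and 4/12 (33%) at level 4, the posterior median MTD is 41.4 Gy with a 50 Gy bound. That still points above the range after a third of level-4 patients had DLTs.

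**Conclusion.** The point holds in conditional form. When the branch is triggered, the excess over 24 is 0, 3, 6 or 9 patients, depending only on how many cohorts were already at level 4. This assumes that those patients count towards the 12 and that replacements are left out. The fixed 24 is therefore not always what the design delivers, and the probability cannot be derived from the documents.

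On the same branch the label goes further than the 25% target supports, since even 0/12 leaves DLT rates up to 26.5% inside the two-sided interval. It is a conflict between two definitions, together with a conclusion drawn too early. It does not show that 40 Gy would be unsafe or unsuitable to carry forward. The correction is inexpensive and touches a primary endpoint, so it should be made.

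**What to change.** (a) In 5.2 and the precis, give the size as 24, or up to 33 if the level-4 expansion is triggered, replacements not counted. In 3.2, say that the 12 include patients already treated at level 4.

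(b) In 3.2, replace the designation of level 4 as the MTD with: *the MTD was not reached; 40 Gy is the maximum dose tested*. Draw this conclusion only after the expansion patients' 4-month assessment, and report it with the level-4 DLT count and exact two-sided 95% CI. If the level-4 DLT rate is then at or above 25% (3 or more of 12), do not use that wording; select the MTD from Table 1 using all data. Put a matching exception in 3.8.1 so that its 2-of-6 rule does not contradict 3.2.

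No change to the EWOC prior is required. The cost is wording in four places, with no patients beyond those the existing clause already calls for. The downsides are a less favourable headline and a less tidy sample-size statement.
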